We have developed a video decision aid for AYAs and their caregivers that reviews treatment options and begins to discuss goals and preferences for their care. The overall objective of this study is to conduct a randomized controlled trial of the video (vs. usual care) in 50 dyads of AYA with advanced cancer and their caregivers. Our hypothesis is that the video better informs patients and caregivers of their options, leads to more ACP conversations, engagement and documentation, and leads to more congruent decision making between AYA and caregivers (primary outcome). Demonstrating the effectiveness of using a video aid in this pilot provides evidence for conducting a larger trial integrating such a video into clinical practice. The

Specific Aims are:

Aim 1: To compare knowledge, preferences and decisional conflict among 50 dyads of AYA with advanced cancer and their caregivers randomly assigned to one of two ACP modalities: 1. The newly created video depicting various goals of care (intervention, 25 dyads), or 2. usual care (control, 25 dyads).

Hypothesis H1a: Patients and caregivers randomized to the video will have higher congruence of preferences between patient and caregiver dyads compared to dyads in the control group (primary outcome). H1b: Those randomized to the video group will have

higher knowledge, fewer preferences for life-prolonging interventions and lower decisional conflict than those randomized to the control group.

Aim 2: To compare ACP conversations between patients with their health care team and caregivers, and ACP documentation between intervention and control dyads. H2: Patients randomized to the video will have more ACP conversations and higher levels of engagement, and more ACP documentation after 3 months.

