Aim 1: H1: AYA with advanced cancer and caregivers randomized to the video will have higher concordance between patients and caregivers (Primary Outcome), and more likely to have higher knowledge, make decisions for less burdensome care (i.e., limited or comfort care, no CPR, no ventilatory support), have lower decisional conflict, and engagement, than those randomized to the control group. Preference concordance between patient and caregiver will be treated as a dichotomized variable and compared between the two study arms using a chi-square test. We will conduct separate analyses for patients and caregivers for secondary outcomes. Knowledge score, decision conflict scale, and ACP engagement will be considered as continuous variables. We will use twosample t-tests or Wilcoxon rank sum tests, whichever more appropriate, to compare the distribution between the two study arms. Chi-square tests will be used to compare the proportion of patients/caregivers choosing less burdensome care between the two study arms. We will explore the effect of patient characteristics (age, sex, etc.) in choosing less invasive care using a logistic regression model. In this study, we will treat sex as selfreported gender and will conduct a sex-based analysis of intervention effects to explore sex as a biological variable. *Power analysis*: Assuming 50% of control arm achieve preference concordance between patients and caregivers, the study will have 80% power to detect a 41% difference (50% vs. 89%) in concordance. Assuming 68% of control patients/caregivers choose non-life prolonging care, the study will have 82% power to detect a 31% difference (68% vs. 99%) in preferences between the two arms. For the continuous outcomes (knowledge, decisional conflict, ACP engagement), the study will have 80% power to detect an effect size of 0.81 with 25 subjects per group.

Aim 2: *H2.* Patients randomized to the video will have more ACP conversations and documentation after 3 months. We will treat conversations and documentation as continuous variables. Assuming 50% of controls achieve ACP conversations/documentation between baseline and three-month follow-up, the study will have 81% power to detect a 27% difference (50% vs. 77%) between the two study arms.

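### Aim 2's stated 81% power (50% vs 77%) needs about 50 patients per arm; with the planned 25 it is about 42–54%, and the outcome is called continuous but powered as a proportion

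*Combined protocol and SAP*

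**What the plan says.** Section 1.0 (Objectives, Aim 1) assigns 25 dyads to the video and 25 to usual care. The Aim 1 power text, in the Data Analyses part of section 8.0, uses the same number: "the study will have 80% power to detect an effect size of 0.81 with 25 subjects per group". Each dyad contains one patient.

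Hypothesis H2, in section 1.0 and again in Data Analyses, is about patients: those given the video are expected to have more ACP conversations and documentation after 3 months. For these outcomes Data Analyses makes two statements in succession. The first fixes the variable type: "We will treat conversations and documentation as continuous variables". The second takes a control proportion of one half by 3 months and gives the power on that basis: "the study will have 81% power to detect a 27% difference (50% vs. 77%) between the two study arms". No sample size, significance level or test is named for Aim 2. The Missing Data paragraph expects some non-completion at 3 months, gives no rate, and starts from the completers.

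**The concern.** Two statements in one section conflict. At the same 50% control rate, Aim 1 puts 80% power at 50% versus 89%, while Aim 2 claims 81% power for the much smaller contrast of 50% versus 77%. With 25 per arm in both cases, these cannot both be right. Separately, a percentage of patients who achieve a conversation or a document is a yes/no outcome, so the Aim 2 power does not belong to the continuous analysis announced just before it.

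Aim 2 is one of two Specific Aims, and section 1.0 presents the pilot as evidence for a larger trial. A reader told that power is 81% could take a null Aim 2 result as evidence that the video does not change conversations or documentation. At the actual sample size, a true 27-point effect would be missed about half the time.

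**Working it through.** **Inputs.** Control proportion p1 = 0.50 and video proportion p2 = 0.77 (Data Analyses, Aim 2). n = 25 patients per arm (section 1.0; Aim 1 power text). The significance level is not stated; two-sided 5% is assumed and varied below.

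**Formula.** Normal approximation with pooled variance under the null:

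power = Φ{ [ (p2 − p1) − 1.96 × √(2·p̄·(1 − p̄)/n) ] / √( [p1(1 − p1) + p2(1 − p2)]/n ) }

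Here p̄ = (0.50 + 0.77)/2 = 0.635, 2·p̄·(1 − p̄) = 0.4636, and p1(1 − p1) + p2(1 − p2) = 0.2500 + 0.1771 = 0.4271.

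**Step 1: reproduce the plan's figure.** With n = 50 per arm: (0.27 − 1.96 × 0.0963)/0.0924 = 0.879, and Φ(0.879) = 81.0%. The exact power of the uncorrected chi-square test at 50 per arm is 81.3%. Solving the formula for 81% power gives 50 per arm (58 with a continuity correction).

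**Step 2: the planned size.** With n = 25 per arm: (0.27 − 1.96 × 0.1362)/0.1307 = 0.024, and Φ(0.024) = 51.0%.

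**Step 3: other tests.** The exact figures enumerate all 2×2 tables.

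| 25 per arm, two-sided 5% | 50% vs 77% (Aim 2) | 50% vs 89% (Aim 1) |
|---|---|---|
| Normal approximation | 51.0% | 87.3% |
| Chi-square, exact power | 54.2% | 89.1% |
| Fisher's exact test | 41.6% | 80.3% |

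No row gives about 80% in both columns. The Aim 1 figures do fit 25 per arm at two-sided 5%: Fisher gives 80.3% for 50% versus 89% and 82.3% for 68% versus 99%, and a t-test gives 80.1% for effect size 0.81. Aim 2 is the figure that does not fit. (Aim 1 labels its contrast a 41-point difference, but 89 − 50 = 39. Reading it as 91% would widen the conflict.)

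**Step 4: significance level and method.** At 25 per arm, a continuity-corrected approximation gives 38.9%. One-sided 5% gives 52–66% across methods. A two-sided level of 20% gives 76.8% by the normal formula, still below 81%.

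**Step 5: detectable difference.** With 25 per arm and 80% power, against 50% in controls, the video arm must reach 85.4% (exact chi-square), 86.1% (normal) or 88.9% (Fisher). That is a difference of about 35, 36 or 39 points.

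**Step 6: loss by 3 months (assumed rates).** With 10%, 20% and 30% lost, power by the normal formula is 46.7%, 42.3% and 37.7%. At 20% loss (20 per arm), exact chi-square gives 43.5% and Fisher 32.2%.

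**The case against.** **Caregivers are also asked about conversations**, so there could be 50 respondents per arm. That is true, and it is as good a numerical explanation of the 81% as the trial's total of 50 dyads; the documents do not show which was used. It does not rescue the figure. H2 is about patients, Data Analyses specifies separate patient and caregiver analyses for secondary outcomes, and documentation exists once per patient. The two members of a dyad are also not independent. With an assumed within-dyad correlation of 0.5, the effective size is 50/1.5 ≈ 33 per arm and power is 55% (Fisher) to 66% (chi-square). With 0.3, it is 50/1.3 ≈ 38 per arm and about 70% by the normal formula.

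**The significance level is assumed, and the two aims' figures reproduce under different tests** (Fisher for Aim 1, chi-square or normal for Aim 2). Both remarks are correct. The requirement of 50 per arm is likewise a chi-square or normal figure; Fisher at 50 per arm gives 75.3%. But no single test reconciles the two claims at 25 per arm, and one-sided 5% does not reach 81%.

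**This is a pilot and Aim 2 is not primary.** Section 2.0 says the 3-month conversations and documentation will be explored, although Table 1 lists conversations as a secondary outcome. This limits the consequences and supports presenting Aim 2 as exploratory. It does not make the stated power correct.

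**Attrition need not affect both outcomes.** Documentation comes from the medical record, so missed telephone interviews need not remove it. The loss scenarios apply chiefly to conversations, and to documentation only if the completer set is used for it.

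**A continuous measure is also possible.** More conversations could mean a count. That is a legitimate choice, but the power statement would then have to be for a count.

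**Conclusion.** The concern holds. With 25 patients per arm, power for 50% versus 77% is about 51–54% by the normal approximation or chi-square test and 42% by Fisher's exact test, against a stated 81%: an overstatement of roughly 27 to 39 percentage points. This assumes a two-sided 5% level, which the Aim 1 figures imply, and no loss to follow-up. The conclusion does not depend on how the 81% arose. That 50 was used as the per-arm number is an inference from the match. The clash between a continuous outcome and a power statement in proportions is plain in the text and needs no assumption. The primary outcome and the sample size are not affected.

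**What to change.** In Data Analyses, Aim 2:

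1. Replace the power sentence with one for 25 patients per arm, naming the test and significance level: at two-sided 5%, 50% versus 77% has about 54% power (chi-square) or 42% (Fisher). The difference detectable with 80% power is about 35–36 points (chi-square or normal) or 39 points (Fisher), before attrition. State an assumed 3-month loss for the interview-based outcome.
2. Describe Aim 2 as exploratory, in line with section 2.0, and report the risk difference with its 95% confidence interval. At 50% and 77% with 25 per arm, the half-width is 1.96 × √(0.4271/25) = 0.256, or about ±26 points, which shows how little a null result would rule out.
3. Make variable type, test and power agree. The simplest way is two patient-level yes/no outcomes (any ACP conversation; any new ACP documentation) compared as proportions, as the power statement already assumes. If a count is preferred, define it, name its test and give an effect size for it.
4. State that caregiver reports of conversations are analysed separately and do not add to the patient sample size.

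The cost is protocol wording and a less favourable stated power. No extra patients or data are needed.

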9.0 Risks to Subjects

Limitations, potential problems, and alternative strategies: (1) We are limiting this study to English-speaking patients because our video is only available in this language presently. Should the study prove successful, we will adapt the video into other languages. (2) Another potential limitation we considered in developing this study proposal pertains to the lack of blinding of research investigators and clinicians to the intervention assignment, which may introduce bias. Blinding research staff to the intervention assignment is not practical and rarely accomplished in ACP trials. *We have implemented rigorous procedures to minimize the risk of bias*.

Subjects may feel uncomfortable while watching the video or during the interview. Subjects will always have the option of taking a break at any point during the study or not answering a question that may provoke anxiety or distress. Additionally, all subjects will also have the option of terminating the study at any point if feeling uncomfortable throughout the study.

Procedures to Minimize Risk: Subjects are informed that they may refuse to answer any questions if they wish and may choose to stop participating at any time. Effort is taken to identify and minimize the risk of emotional distress for study participants in a standardized fashion

10.0 Potential Benefits to Subjects

This project's results will investigate preferences that lead to decision-making in EOL care. AYAs and their caregivers may uniquely benefit from use of visual video technology to augment the ACP process. The minimal risk of potential psychological distress that may be provoked with discussing decision-making is clearly outweighed by the benefits and impact of this study's results.

11.0 Vulnerable Populations

Inclusion of Women and Minorities: This study does not focus on any race, ethnicity, or gender. No potential research subjects will be excluded from enrollment based on race, ethnic origin, or gender. Patients will be recruited from patients at DFCI/BCH/BWH that have advanced cancer and are expected to reflect the racial and ethnic diversity of this hospital-based population.

12.0 Setting

Research sites will include Dana-Farber/Boston Children's Hospital and Brigham and Women's Hospital as well as Massachusetts General Hospital.

13.0 Recruitment Methods

- 13.1 Patients will be recruited in the inpatient units, outpatient oncology clinics, or over the phone. The RA will approach or call the patient and ensure they have sufficient time to hear about the study and review the consent form if needed (Approach script, Appendix K). If potential participants are contacted virtually, the RA will call them up to three times approximately one week after the pre-notice letter is mailed. If the participant is interested, we will send them a consent form to review. Before the scheduled Zoom visit, we will ask if they have any questions and ask for verbal consent from the AYA.
- 13.2 Patients between the ages of 18-390 on the inpatient and outpatient rosters of all sites will be screened on a regular basis, and additional potential participants will be identified through collaboration with the center for young adult oncology (CAYAO) and the Young Adult Program (YAP).
- 13.3 Information about the study and along with the study team's contact information may be included in patient-facing materials (newsletters, young adult program (YAP), application, fliers) to help spread awareness and better identify eligible participants.
- 13.4 We may also ask providers if any of their patients would be good candidates for this study.
- 13.5 For any subject who is being seen in clinic on the day of screening or who is admitted to the oncology services and is between the ages of 18-39, the RA will open their record and review primary language, diagnosis, and disease status. These components will be noted in a tracking log with the patient's name, MRN, and date of birth. If the patient meets all eligibility requirements, an opt-out email will be sent to the primary oncology attending. If the oncologist has not responded within 72 hours or gives permission to approach, the RA will plan to approach the family. Additionally, the study team at DFCI will receive a list of eligible patients, who have passed the provider opt-out phase, from Massachusetts General Hospital for which the Dana-Farber staff will mail a letter to and approach for research participation.
- 13.6 The RA will plan to approach the patient at their next clinic appointment, or if they are inpatient, at their next available opportunity. If it is not possible to reach them in-person, the RA will

call them. Up to 3 attempts at contacting eligible participants will be made. They will be given a brief overview of the study.

13.7 Participants who complete all study materials will be given an \$20 Amazon gift card. Participants that complete follow-up interview questions will receive an additional \$10 Amazon gift card.

14.0 Consent Process

This study contains no more than minimal risk and written consent or verbal consent will be obtained from each study participant. Consent will be obtained by the RA in outpatient clinics, inpatients units at DFCI/BCH/BWH/MGH, or over the phone/Zzoom. Prior to explaining the study, the RA will ensure that the time and location are okay. Eligible patients will not be approached if the RA or provider considers them to be in a time of high stress. If inpatient, consent will be obtained in the patient's room. In the outpatient clinic, exam rooms, infusion suites, consult rooms, or quiet areas of the waiting area may be used. If the patient is interested in participating, consent may occur at the time of study introduction, or if they would like to take time to think about participating, a follow-up meeting will be scheduled. The RA will follow the processes outlined in "Policy: Informed Consent Process (CON-100)" to obtain informed consent (Appendix L).

We request a waiver of documentation of consent for participants that are accrued virtually because the study presents no more than minimal risk and all study procedures will be deidentified.

We also request a waiver of documentation of consent for oncology providers who participate given that their participations represent no more than minimal risk and their recordings/surveys will be deidentified.

